5.6 Required Premedication and Post-medication

All subjects enrolled will receive premedication consisting of dexamethasone orally (PO) at 8 mg BID given on Day -1, Day 1 (the day of dosing), and Day 2 of each rovalpituzumab tesirine cycle. Dexamethasone will be provided through a subject's local prescription by investigator or other provider (i.e., dexamethasone will not be provided by the sponsor). When dexamethasone is not available, the glucocorticoid-equivalent dose of an alternate corticosteroid may be administered. Parenteral (e.g., intravenous, IV) administration may be substituted for per os (by mouth/orally, PO) at the discretion of the investigator.

On Day 1 of each rovalpituzumab tesirine cycle, the first dose of dexamethasone of the day must be taken at least 30 minutes, but no more than 4 hours, prior to the rovalpituzumab tesirine infusion. In the event that a subject arrives for administration of study drugs on Day 1, but has not taken any or all required dexamethasone doses on Day -1 and/or Day 1, study drug administration may proceed, at the investigator's discretion, after administration of a parenteral corticosteroid dose equivalent to the total missed dexamethasone dose prior to administration of study drugs. For instance, subjects who missed 1, 2, or 3 dexamethasone doses could receive 43 mg, 85 mg, or 128 mg methylprednisolone IV, respectively, prior to proceeding with administration of study drugs. If a subject misses any dose(s) of dexamethasone prior to these visits, the medical monitor may be consulted if additional guidance is needed.

5.7 Prior and Concomitant Therapy

Any medication or vaccine (including over-the-counter or prescription medicines, vitamins and/or herbal supplements) that the subject is receiving at the time of enrollment, or receives during the study, must be recorded along with the reason for use, date(s) of administration including start and end dates, and dosage information including dose, route and frequency.

Any concomitant therapy given for a study protocol-related AE should be recorded from the time of informed consent.

5.7.1 Required Concomitant Therapy

Other than dexamethasone (Section 5.6), there are no required concomitant therapies. However, due to the potential for rovalpituzumab tesirine-related skin photosensitivity, subjects should be

advised to avoid unprotected sun exposure and use a broad spectrum sunscreen (sun protection factor [SPF] of at least 30), protective clothing, a broad-brimmed hat, and sunglasses when outdoors or when driving or riding in the car for more than 1 hour, with re-application of sunscreen as activity-appropriate.

5.7.2 Allowed Concomitant Therapy

Standard supportive care for drug-related toxicity is permitted, including growth factors and blood product transfusions per local institutional standards. Other standard supportive care for symptom control or drug-related toxicity is allowed, such as analgesics, anti-emetics, electrolyte replacement, and hydration. Bone modifying agents for bone metastases are also permitted per local institutional standards. Other prescribed medications for non-neoplastic conditions are allowed, as well as vitamins and nutritional supplements.

Concomitant prednisone (or equivalent) may be used at a dose of ≤ 20 mg/day. The use of intermittent high-dose corticosteroid treatment to prevent or manage hypersensitivity reactions, serosal effusions (Section 8.3.1), or other non-cancer-related symptoms including premedication for known hypersensitivity reactions to contrast for scans is allowed.

Routine prophylaxis with vaccines is permitted; however, vaccines used should not contain live micro-organisms.

If the subject is taking chronic suppressive anti-infectives (antiviral, antifungal, or antibacterial), appropriate investigation must be completed prior to registration and documentation must exclude active infection. The subject should continue suppressive anti-infectives for the duration of study participation.

5.7.2.1 Palliative Therapy

Palliative (limited-field) radiation therapy and palliative surgical resection are permitted if the following criteria are met:

- The subject is considered to have progressed at the time of palliative therapy and meets criteria to continue with treatment beyond progression (Section 7.2.1).
- The case is discussed with the sponsor, medical monitor (or designee). Palliative therapy must be clearly documented as such in the study record.

5.7.2.2 Surgical Resection Following Initial Response

Investigators may choose to resect solitary lesions and render the subject free of macroscopic disease. Subjects enrolled in this study may have such lesions surgically resected only following

consultation with the medical monitor and following the Week 12 re-staging assessments. If tumor shrinkage of the solitary lesion is noted on the re-staging assessment (e.g., Week 12), it is highly encouraged that surgical resection be delayed until subsequent confirmatory scans confirm response, and/or fail to demonstrate further shrinkage. Subjects with a PR who go on to have surgical resection of remaining disease will be considered a PR. Tumor tissue of any resected solitary lesion should be submitted to AbbVie. Detailed instructions of the obtaining, processing, labeling, handling, storage and shipment of these specimens will be provided in a separate Laboratory Manual.

5.7.3 Prohibited Concomitant Therapy

Subjects may not receive other investigational drugs, immunosuppressive medications, radiotherapy, or systemic anti-neoplastic therapy during the study, other than as allowed in Sections 4 and 5.7.2. Subjects may not have received any systemic anticancer therapy (e.g. chemotherapy, small molecule inhibitors, radiation, and/or other investigational anticancer agents) within two weeks of the Screening Visit.

5.8 Treatment Compliance

Study drug administration must be performed by study site staff and documented in source documents and the eCRFs.

5.9 Study Drug Accountability

The director of the medical institution should appoint a study drug management director. The investigator and the study drug management director will maintain accurate records of receipt and the condition of all study drugs including dates of receipt. In addition, accurate records will be kept of the weight used to calculate each dispensed rovalpituzumab tesirine dose, and when and how much study drug is dispensed and used by each subject in the study. Any reasons for departure from the protocol dispensing regimen must also be recorded.

Drug accountability records and inventory will be available. Remaining study drugs (all used, partially used, and unused vials) will be returned to AbbVie or its specified designee/depot or destroyed at the site according to applicable regulations.

Study drugs must not be used for any purpose other than the present study.

Further instructions about study drug accountability are detailed in the Pharmacy Binder.

5.10 Contraception Recommendations

If female, subject must be either postmenopausal or permanently surgically sterile (refer to inclusion criteria for definitions of both), OR a Woman of Childbearing Potential, practicing at least one of the following methods of birth control, on Cycle 1 Day 1 (or earlier) through at least 31 weeks after the last dose of study drug.

If subject is a Woman of Childbearing Potential practicing acceptable birth control, one of the following methods must be followed starting on Day 1 (or earlier) through at least 31 weeks following the last dose of study drugs:

- Combined (estrogen and progestogen containing) hormonal contraception (oral, intravaginal, transdermal) associated with the inhibition of ovulation, initiated at least 1 month prior to study Day 1.
- Progestogen-only hormonal contraception (oral, injectable, implantable) associated with inhibition of ovulation, initiated at least 1 month prior to study Day 1.
- Bilateral tubal occlusion/ligation.
- Vasectomized partner(s), provided the vasectomized partner has received medical assessment of the surgical success and is the sole sexual partner of the woman of child bearing potential trial participant.
- Intrauterine device (IUD).
- Intrauterine hormone-releasing system (IUS).
- True abstinence: Refraining from heterosexual intercourse – when this is in line with the preferred and usual lifestyle of the subject. (Note: periodic abstinence [e.g., calendar, ovulation, symptothermal, post-ovulation methods] and withdrawal are not acceptable).

Male subjects who are sexually active with a woman of childbearing potential, even if the male subject has undergone a successful vasectomy, must agree from Study Day 1 through at least 31 weeks after the last dose of study drug to use condoms and his female partner(s) must use at least one of the contraceptive measures (as defined in the protocol for female study subjects of childbearing potential).

Male subject agrees not to donate sperm from Study Day 1 through at least 31 weeks after the last dose of study drug.

5.11 Documentation of Non-Childbearing Status and Pregnancy Testing

For each female subject, the Investigator will document non-childbearing status (surgically sterile or post-menopausal for at least 1 year) or potential childbearing status.

Should a female study subject become pregnant or suspect she is pregnant while participating in this study, she should inform the treating Investigator immediately (Section 8.3.8).

For female subjects of childbearing potential, the laboratory will perform pregnancy testing according to Appendix 13.1. A serum pregnancy test will be performed at Screening and the results must be available prior to the administration of the first dose of investigational product on C1D1. Subjects with borderline pregnancy tests at Screening must have a serum pregnancy test ≥ 3 days later to document continued lack of a positive result. Urine pregnancy tests will be performed at Day 1 of each cycle and again at the End of Treatment Visit.

Females of non-childbearing potential (either postmenopausal or permanently surgically sterile) as defined in Section 4 at Screening do not require pregnancy testing. Post-menopausal female subjects ≤ 55 years of age must have an FSH level >40 IU/L and will have FSH performed at Screening and assessed by the Investigator.

6. Study Activities

6.1 Enrollment

Subjects who provide informed consent will be screened for eligibility. Once screening procedures have been completed, and for those subjects who meet all of the entry criteria, a Registration and Enrollment Form will be completed and submitted to the sponsor or designee to confirm eligibility. Approved subjects will then be enrolled into a treatment cohort. Refer to the Study Binder for the enrollment form, contact numbers, and other details of enrollment.

Safety assessments (Section 2.4.1) will include physical examinations, vital signs, body weight, ECOG performance status, AE assessments, laboratory tests (Section 7.7.3), ECGs, echocardiograms, Fluid Retention Questionnaire, concomitant medications, AEs, and concomitant therapies will be recorded from Day 1 (pre-dose) through the safety reporting period. At the same time, subjects will maintain a diary of daily weights. Any protocol-related AE should be recorded from the time of informed consent as well as any concomitant therapies given for treatment of the AE.

Study activities are listed by visit in this section and descriptions of all study assessments are presented in Section 7. A schedule of events is provided in Appendix 13.1.

Subjects undergoing retreatment as described in Section 3.1.2 will follow the same study schedule from Screening through EOT and LTFU.

6.2 Prescreening Visit

Informed consent for the prescreening portion of this study will be obtained in order to collect and test an archived or fresh tumor tissue specimen for DLL3 expression (Section 7.4.1). Up to the first 12 subjects enrolled into each cohort must test positive for the expression of DLL3, per IHC assay criteria. Demographic information will be collected at this visit (Section 7.1).

6.3 Screening Visit (Days -14 to -1)

Informed consent for the main portion of this study will be obtained prior to the performance of any study procedures and may occur within 30 days prior to the Day 1 Visit. All other screening procedures must occur within 14 days prior to Day 1. Imaging performed as standard of care within 14 days prior to Day 1 will be accepted.

The following assessments will occur during Screening:

- Informed consent – omitted for retreatment subjects

- Demographics (Section 7.1) – omitted for retreatment subjects
- Confirmation of study eligibility per inclusion/exclusion criteria (Section 4); if prescreening visit was not conducted, testing of an archived or fresh tumor tissue specimen for DLL3 expression will be conducted during the Screening Visit. Upon enrollment into the study, remaining tumor tissue will be analyzed for PD-L1 expression.
- Medical and surgical history (Section 7.1) – omitted for retreatment subjects
- Malignancy history (Section 7.1) – omitted for retreatment subjects
- Prior anticancer treatments (Section 7.1) – omitted for retreatment subjects
- Physical examination (Section 7.7.1)
- Vital signs (Section 7.7.2)
- Height (Section 7.7.2) (For adult subjects (≥ 18 years), measurements of height obtained within 6 months prior to Screening Visit may be utilized)
- Urinalysis (Section 7.7.3)
- Triplicate electrocardiogram (ECG)
- ECOG performance status (Section 7.7.6 and Appendix 13.3)
- Procedure-related AEs (Section 7.6)
- Procedure-related concomitant medications
- Disease assessment consisting of CT scans of the chest, abdomen, and pelvis (and neck if indicated) (Section 7.2) – may be omitted for all subjects if recent scans demonstrating PD are within 14 days prior to dosing of study drugs.
- Magnetic resonance imaging (MRI) of the brain – may be omitted for all subjects if recent scans are taken within 14 days prior to dosing of study drugs. CT of the brain with IV contrast may be substituted at the discretion of the investigator. (Section 7.2)
- Paraneoplastic Assessment (Appendix 13.8)
- Blood sample collection for:
 - Complete blood count (CBC) with differential (Section 7.7.3)
 - Serum chemistries (Section 7.7.3)
 - Coagulation tests (Section 7.7.3)
 - Hepatitis B and C tests (Section 7.7.3) – omitted for retreatment subjects
 - Pregnancy test (serum) (Section 7.7.3) for women of child-bearing potential

- Blood ██████████ (Section 7.4.2)
- Blood soluble markers (Section 7.4.3)
- Flow cytometry (Section 7.4.4)
- Peripheral blood RNA (Section 7.4.5)
- Genotyping (Section 7.4.8)
- Endocrinology tests, including ACTH, thyroid stimulating hormone (TSH), and free thyroxine (T4)

6.4 Treatment Period

Treatment will be administered in 3-4 week cycles.

6.4.1 Peridosing with Dexamethasone

6.4.1.1 Day –1 (Day before Dosing) of Cycle 1 and Cycle 3 Only

- Subjects will take dexamethasone 8 mg PO BID (Section 5.6).
- Dexamethasone may be taken at home or in the clinic.

6.4.1.2 Day 1 (Day of Dosing) of Cycle 1 and Cycle 3 Only

- Subjects will take dexamethasone 8 mg PO BID (the first dose of the day should be at least 30 minutes, but no more than 4 hours, prior to the rovalpituzumab tesirine dose); this dose of dexamethasone will be taken in the clinic.
- All subjects will receive 0.3 mg/kg of rovalpituzumab tesirine at Cycle 1 Day 1 and Cycle 3 Day 1 (Week 7).

6.4.1.3 Day 2 (Day After Dosing) of Cycle 1 and Cycle 3 Only

- Subjects will take dexamethasone 8 mg PO BID (Section 5.6)

6.4.2 Day 1 Visit (±2 days) of Each Cycle

If Screening activities occur within 1 calendar day prior to Cycle 1 Day 1, the following pre-dose assessments do not need to be repeated at the Cycle 1 Day 1 Visit: physical examination, ECOG performance status, local safety labs (CBC with differential, chemistries, coagulation tests, urinalysis, and pregnancy test), and disease assessment with tumor response on cycles where imaging is required.

Day 1 procedures may be performed up to 2 calendar days prior to dosing of study drugs. Results from local clinical laboratory tests (at least CBC with differential and serum chemistry panel)

and disease assessment with tumor response on cycles where imaging is required must be available prior to dose administration. All assessments must occur prior to dosing (Appendix 13.1). Imaging report confirming measurable or evaluable disease from the central reader will be provided to determine eligibility prior to enrollment.

The following will be performed on the Day 1 Visit of each cycle:

- Physical examination (Section 7.7.1)
- Vital signs – within 30 minutes prior to the infusion, and then post-infusion at 30 minutes (± 10 minutes), 2 hour (± 15 minutes), and 4 hour (± 30 minutes) for Cycles 1 and 3 only. For all other cycles, vital signs should be collected at least 30 minutes (± 10 minutes), but no longer than 4 hours prior to infusion (Section 7.7.2). Post-infusion vitals do not need to include weight. Weight needs to be collected only once prior to infusion and does not need to be collected within 30 minutes prior to infusion.
- Urinalysis (Section 7.7.3)
- Pregnancy test (urine) (Section 7.7.3) for women of child-bearing potential
- Triplicate ECG prior to infusion of rovalpituzumab tesirine and then post-infusion at 30 minutes ± 10 minutes (only done on Cycles 1 and 3) (Section 7.7.4). Triplicate ECG should be performed prior to PK draw.
- Echocardiogram (only performed at Cycles 1 and 3 (cycles where rovalpituzumab tesirine is administered) (Section 7.7.5)
- ECOG performance status (Appendix 13.3)
- Fluid Retention Questionnaire with daily weight diary accountability (Cycles 1, 2, 3, and 4) (Section 7.7.7)
- Record all AEs and SAEs (Section 7.6)
- Record concomitant medications
- Blood sample collection for:
 - CBC with differential (Section 7.7.3)
 - Serum chemistries (Section 7.7.3)
 - Coagulation tests (Section 7.7.3)
 - Rovalpituzumab tesirine PK (Section 7.3)
 - Prior to infusion – on Cycle 1 Day 1, Cycle 3 Day 1, and Cycle 5 Day 1

- Post-infusion at 30 minutes (\pm 10 minutes), 2 hours (\pm 15 minutes), and 4 hours (\pm 30 minutes) – only on Cycle 1 and Cycle 3.
- Rovalpituzumab tesirine ATA –prior to infusion only on Cycle 1 Day 1, Cycle 3 Day 1, and Cycle 5 Day 1
- Nivolumab PK and ATA – all cycles (prior to infusion)
- Ipilimumab PK and ATA (Cohorts 2 and 3 only) – on Cycle 1 Day 1, Cycle 2 Day 1, Cycle 3 Day 1, Cycle 4 Day 1, Cycle 5 Day 1, and Cycle 6 Day 1 (prior to infusion)
- Endocrinology tests, including ACTH, thyroid stimulating hormone (TSH), and free thyroxine (T4)
- Blood [REDACTED] (Section 7.4.2)
- Blood soluble markers (Section 7.4.3)
- Flow Cytometry (Section 7.4.4)
- Peripheral blood RNA (Section 7.4.5)
- CTCs – (C1D1 and C5D1 pre-infusion only) (Section 7.4.6)
- Plasma for ctDNA (Cycle 1 Day 1, pre-dose only) (Section 7.4.7)
- Administration of study drugs (Section 5.1); on applicable cycles, rovalpituzumab tesirine will be administered before nivolumab and ipilimumab. Similarly, on applicable cycles, nivolumab will be administered prior to ipilimumab.
- Serosal fluid collection, if applicable (Section 7.4.9)

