6.4.3 Day 2 (Day After Dosing) of Cycle 1 and Cycle 3 Only

- Record AEs and SAEs (Section 7.6) – may be collected by telephone.
- Record concomitant medications – may be collected by telephone.
- A single rovalpituzumab tesirine PK draw will be obtained 24 hours (\pm 2 hours) after start time of infusion of rovalpituzumab tesirine on Day 1.

6.4.4 Days 8 and 15 Visits (\pm 2 days) of Cycle 1 and Cycle 3

The following assessments will be performed at Cycle 1 (Day 8), Cycle 1 (Day 15), Cycle 3 (Day 8) and Cycle 3 (Day 15) (\pm 2 days):

- Physical examination (Section 7.7.1)
- Vital signs (Section 7.7.2)
- Urinalysis (Section 7.7.3)

- Fluid Retention Questionnaire with daily weight diary accountability (Section 7.7.7)
- Record AEs and SAEs (Section 7.6)
- Record concomitant medications
- Serosal fluid collection, if applicable (Section 7.4.9)
- Blood sample collection for:
 - CBC with differential (Section 7.7.3)
 - Serum chemistries (Section 7.7.3)
 - Rovalpituzumab tesirine PK

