6.5 End of Treatment Visit

The EOT Visit occurs within 7 days of documentation of the decision to discontinue treatment. The following procedures will be performed at the EOT Visit:

- Physical examination (Section 7.7.1)
- Vital signs (Section 7.7.2)
- Urinalysis (Section 7.7.3)
- Pregnancy test (urine) (Section 7.7.3) for women of childbearing potential
- Triplicate ECG (Section 7.7.4)

- Echocardiogram (Section 7.7.5)
- ECOG performance status (Appendix 13.3)
- Record AEs and SAEs (Section 7.6)
- Fluid Retention Questionnaire with daily weight diary accountability (Section 7.7.7) if EOT occurs prior to Cycle 5
- Record concomitant medications
- Disease assessment consisting of CT scans of the chest, abdomen, and pelvis (and neck if indicated) – may be omitted if a Disease/Response Assessment was performed within the last 6 weeks (Section 7.2)
- MRI of the brain – if clinically indicated (e.g., if CNS progression has been documented previously); may be omitted if a Disease/Response Assessment was performed within the last 6 weeks. CT of the brain with IV contrast may be substituted at the discretion of the investigator (Section 7.2).
- Blood samples for:
 - CBC with differential (Section 7.7.3)
 - Serum chemistries (Section 7.7.3)
 - Coagulation tests (Section 7.7.3)
 - Rovalpituzumab tesirine PK and ATA
 - Nivolumab PK and ATA
 - Ipilimumab PK and ATA
 - Blood ██████████ (Section 7.4.2)
 - Plasma for ctDNA (Cycle 1 Day 1, pre-dose only) sample
 - Blood soluble markers (Section 7.4.3)
 - Flow Cytometry (Section 7.4.4)
 - Peripheral blood RNA (Section 7.4.5)
 - CTCs (Section 7.4.6)
 - Endocrinology Tests, including ACTH, thyroid stimulating hormone (TSH), and free thyroxine (T4)
- (Optional) fresh tumor tissue, collected at disease progression (Section 7.4.1)
- Serosal fluid, if applicable (Section 7.4.9)

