7.7.7 Fluid Retention Questionnaire with Daily Weight Diary

Throughout the treatment period, subjects will be asked about the development of any new or worsening peripheral edema or dyspnea (Appendix 13.9). This assessment may take place via telephone.

Throughout the treatment period (starting with Day 1 pre-dose through the end of Cycle 4), subjects will maintain a diary of daily weights.

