 - 21) Echocardiogram includes assessment of LVEF and pericardial effusion, if present; performed only on Cycles 1 and 3 when rovalpituzumab tesirine is administered. ECHO may be performed up to 72 hours prior to Rova-T administration.
 - 22) Fluid Retention Questionnaire includes diary of daily weights and queries for worsening/ new edema or dyspnea; Fluid Retention Questionnaire will be administered on Cycles 1, 2, 3, 4 and EOT visit if occurs prior to Cycle 5. Subjects should record daily weight from Day 1 through the end of Cycle 4.
 - 23) Procedure-related AEs (only).
 - 24) Concomitant Medications include names of all concomitant therapies, including dates of administration, dose regimen, route of administration, and purpose.
 - 25) Procedure related concomitant medications (only).
 - 26) CT imaging of the chest, abdomen, and pelvis, and neck (if indicated), for assessment via RECIST v1.1.
 - 27) On applicable cycles, disease assessment will occur at least 3 days but no greater than 7 days prior to day of dosing. See Section 6.4.6 for imaging schedule per cohort.
 - 28) CT of the brain with IV contrast may be substituted at the discretion of the investigator.
 - 29) MRI brain is only required after screening if clinically indicated (e.g. if CNS progression is documented).
 - 30) Cycles 1 and 3 only.
 - 31) Nivolumab will be administered after rovalpituzumab tesirine on applicable cycles.
 - 32) Cycles 2 and 3 only.
 - 33) Cycles 4 and beyond.
 - 34) See Appendix 13.2 for rovalpituzumab tesirine and nivolumab PK time points.
 - 35) Rovalpituzumab tesirine *single* PK will be collected at Cycle 1: Day 2, Day 8, Day 15, Cycle 3: Day 2, Day 8, and Day 15.

-
- 36) Prior to infusion on Cycles 1, 3, 5 only.
- 37) Prior to infusion for all cycles.

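### For subjects who continue into Cycle 5, no scheduled visit reviews the Cycle 4 weight diary and fluid-retention forms

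*Combined protocol and SAP*

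**What the plan says.** The protocol describes the questionnaire and diary in several places.

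- **Day 1 visits (Section 6.4.2):** "Fluid Retention Questionnaire with daily weight diary accountability (Cycles 1, 2, 3, and 4".
- **Mid-cycle visits (Section 6.4.4):** the questionnaire and diary check are among the items under "The following assessments will be performed at Cycle 1 (Day 8), Cycle 1 (Day 15), Cycle 3 (Day 8) and Cycle 3 (Day 15". Cycle 4 has no such visit.
- **EOT (Section 6.5):** "Fluid Retention Questionnaire with daily weight diary accountability (Section 7.7.7) if EOT occurs prior to Cycle 5".
- **Schedule notes (Appendix 13.1; note 22 for Cohort 1, note 26 for Cohorts 2 and 3):** these repeat the limit to Cycles 1 to 4 plus an early EOT, and add "Subjects should record daily weight from Day 1 through the end of Cycle 4".
- **Assessment description (Section 7.7.7):** "Throughout the treatment period, subjects will be asked about the development of any new or worsening peripheral edema or dyspnea". It adds "This assessment may take place via telephone". Its next paragraph has the weight diary run from Day 1 to the end of Cycle 4.
- **Example form (Appendix 13.9):** one form per seven-day period, holding the daily weights and the questions on swelling and shortness of breath.
- **Enrollment section (6.1):** can be read as carrying these assessments through the safety reporting period.

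The washout visits and calls in Section 6.4.5 list neither the questionnaire nor the diary.

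**The concern.** Section 1.4 reports peripheral edema in 23% of subjects and serosal effusions of Grade 3 or higher in 14%, as events considered related to rovalpituzumab tesirine. It gives the questionnaire and daily weights as part of the response to such risks. Section 8.3.1 treats effusions as potentially life-threatening and in need of prompt evaluation. Yet the plan has subjects record data for a full cycle after the last visit at which anyone is assigned to look at them.

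That cycle lies within, or mostly within, the 12-week DLT period of Section 3.1.1. DLT counts in the first 6 evaluable subjects inform cohort expansion and the opening of the next cohort (Section 3.1). Weight gain or a positive answer on a Cycle 4 form could bear on whether an event is recognised and dated within the window. As scheduled, nobody is assigned to collect that form from a subject who continues.

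The sections also differ on how long edema and dyspnea are to be asked about, so sites may run this differently.

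**Working it through.** The documents state no figure for this gap, so there is none to reproduce. The check is calendar arithmetic.

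**Inputs**
- Cycle lengths (Section 5.1.1, Table 2 notes): Cohort 1, Cycles 1 to 3 are 21 days and Cycle 4 is 28 days. Cohorts 2 and 3, Cycles 1 to 5 are 21 days.
- Second rovalpituzumab tesirine dose: Cycle 3 Day 1 (Section 6.4.1.2).
- Scheduled reviews: Day 1 of Cycles 1 to 4, and Days 8 and 15 of Cycles 1 and 3.
- DLT window: 12 weeks = 84 days (Section 3.1.1).

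**Cycle start days** (previous start + cycle length)
- Cohort 1: 1, 22, 43, 64, 64 + 28 = 92.
- Cohorts 2 and 3: 1, 22, 43, 64, 64 + 21 = 85.

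**Scheduled review days, all cohorts:** 1, 8, 15, 22, 43, 50, 57, 64.

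| Quantity | Cohort 1 | Cohorts 2 and 3 |
|---|---|---|
| Last scheduled review | Day 64 | Day 64 |
| Days after second dose | 64 − 43 = 21 | 64 − 43 = 21 |
| Last diary day | 92 − 1 = 91 | 85 − 1 = 84 |
| Diary days without scheduled review | 92 − 64 = 28 | 85 − 64 = 21 |
| Share of diary | 28/91 = 31% | 21/84 = 25% |
| Of these, in the DLT window (Days 64–84) | 21 | 21 |

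The ±2-day window on each of the two Day 1 visits widens the 21-day interval after the second dose to about 17 to 25 days. The counts include Day 64. If that day's weight is checked at the visit, the unreviewed days fall by one, to 27 and 20.

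**With a review at Cycle 5 Day 1**
- Days without scheduled review: 28 or 21 becomes 0.
- Scheduled review then reaches 92 − 43 = 49 days (Cohort 1) or 85 − 43 = 42 days (Cohorts 2 and 3) after the second dose.

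**The case against.** The strongest reply is that fluid retention stays under observation after Day 64, and most of that reply stands.

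- **Asking may continue.** The schedule notes describe the questionnaire as including both the weights and the symptom queries, and the example form is weekly. If that form is used, subjects are asked in writing until Day 84 or 91. A reader might infer that solicitation falls to zero after Day 64, but the documents do not support that. What is missing is a scheduled point of review.
- **Subjects who stop are covered.** An EOT visit before Cycle 5 includes the questionnaire and diary check, so it would be wrong to say that nobody's Cycle 4 pages are reviewed.
- **Other checks continue.** Later Day 1 visits include physical examination and clinic weight. All cohorts have CT of chest, abdomen and pelvis 3 to 7 days before Cycle 5 Day 1 (Section 6.4.6): about Days 85 to 89 in Cohort 1 and Days 78 to 82 in Cohorts 2 and 3. Cohorts 2 and 3 also have washout safety visits. It would therefore be wrong to say that only open-ended questioning remains. These checks have limits: examinations after Screening are symptom-directed (Section 7.7.1), and echocardiograms are tied to Cycles 1 and 3 and EOT (Sections 6.5 and 7.7.5).
- **Section 7.7.7 is ambiguous.** Its diary paragraph glosses the treatment period as ending with Cycle 4, and the edema and dyspnea sentence may carry the same meaning. A flat contradiction with the schedule is not established.
- **No bias is shown.** A reader might infer that edema and dyspnea counts must decline over time because of the schedule. No such effect is quantified. Section 10.3.5.1 summarises adverse events by cohort, not by time, and the scheduled review days are identical across cohorts up to Day 64. No planned analysis depends on the questionnaire, so an extra table with a common onset cut-off is not needed to correct one.

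None of this supplies a visit at which a continuing subject's Cycle 4 forms are collected and reviewed.

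**Conclusion.** The gap is real but narrow. For subjects who start Cycle 5, the last 21 diary days (Cohorts 2 and 3) or 28 (Cohort 1) have no scheduled review, and 21 of them fall in the DLT window in every cohort. The wording on when edema and dyspnea questioning ends is unclear across sections and needs reconciling. This review does not say which period is right.

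The figures assume on-schedule cycles. That written symptom answers exist for Cycle 4 assumes that the form in use matches the example in Appendix 13.9, which is marked as an example only. No sample-size or error-rate figure is affected. This is an inexpensive improvement that makes usable the safety data the plan already collects on a leading toxicity.

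**What to change.** 1. Add Cycle 5 Day 1 to the questionnaire and diary-accountability item in Section 6.4.2 and to the schedule notes for all three cohorts, so that Cycle 4 forms are collected and reviewed.
2. Reconcile Sections 6.1, 6.4.2, 6.5 and 7.7.7, the schedule notes and Appendix 13.9 on when edema and dyspnea questioning ends and when the last diary pages are checked.

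The cost is one short check at an existing visit, and Section 7.7.7 already allows the questioning by telephone. The review is retrospective: it follows the previous one by 21 days in Cohorts 2 and 3, the same interval the schedule already has between Day 22 and Day 43, and by 28 days in Cohort 1. In Cohort 1 it falls on Day 92, 8 days after the DLT window closes (92 − 84), so a DLT assessment made before then would not have these pages.
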